6.2.3. Sensitivity Analysis

Sensitivity analysis will be performed for the primary analysis by imputing missing ACT values using the multiple imputation (MI) method assuming missing at random (MAR). Those who discontinue early due to technology failure, disliking the digital platform, disease worsening, adverse experience or disliking the IMP will be considered having missing data. For those who discontinue early not due to these reasons, the ACT value assessed at the ET visit will be used. Those who discontinue early and do not have an ET visit will be considered having missing data.

The following steps will be performed for the analysis:

- Create complete datasets using imputation. The SAS code is as follows:

```
proc mi data = yy out = yy2 seed = 4192 n impute = 500 minimum = 5 maximum = 25;
class trt;
```

```
var trt actbase v2;  
monotone regpmm;  
run;
```

- For each dataset, the clinically important improvement in asthma control variable will be derived for each patient as defined in Section 6.2.1.
- Analyze each dataset using the model described below for the primary endpoint.

```
ods output Diffs = dif LSMeans = lsm;  
proc genmod data = indata;  
by _imputation_;  
class trt;  
model y = trt actbase / dist = binomial;  
lsmeans trt/pdiff cl diff exp;  
run;  
ods output close;
```

- The output datasets from the above analysis will contain odds ratio estimates from each of the 500 datasets. An overall estimate will be generated using PROC MIANALYZE . The SAS code is as following:

```
proc mianalyze data=zz;  
modeleffects estimate;  
stderr stderr;  
ods output paramestimates=or;  
run;
```

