6.2.2. Primary Analysis

To analyze the primary endpoint, the following estimand framework will be used:

1. Analysis will be performed on the mITT analysis set.
2. A binary distribution is assumed for the primary endpoint. Patients who discontinue early due to technology failure, disliking the digital platform, disease worsening, adverse experience or disliking the IMP will be counted as treatment failures. For those who discontinue early not due to these reasons, the ACT value assessed at the ET visit will be used.
3. Summary measure: A successful differentiation between the 2 groups will be determined by a Bayesian posterior probability for $\beta_1 > 0$ greater than 0.95 (1-sided). The following statistical methods will be utilized:

Logistic regression model allowing for different response rates at enrolling investigational centers will be used for testing the hypothesis $H_0: \beta_1 = 0$, $H_1: \beta_1 > 0$ in the following model:

$$\ln\left(\frac{p_{ij}}{1-p_{ij}}\right) = \beta_0 + \beta_1 x_i + \beta_2 \text{baseline ACT value} + \text{Center}_j$$

where x_i = treatment group i , p_{ij} = response proportion of treatment group i at Center j , $Center_j$ = random center effect of center j .

Non-informative priors will be assumed for all coefficients. Estimates of mean response rate and corresponding 95% credible intervals for individual proportions, histograms of the posterior response rates, odds ratio with corresponding 95% credible intervals for DS versus CC, and probability of ($\beta_1 > 0$) and probability of (*Odd Ratio* > clinical meaningful value) will be presented.

The SAS code for the primary analysis is as follows:

```
proc mcmc data = x nbi = 1000 nmc = 500000 thin = 20 seed = 159 outpost =
post1 monitor = (beta0-beta2 sigma2 beta1_gt0 pi pi0 pooled or)
statistics=(summary intervals);
parms beta0-beta2 0;
parms sigma2 1;
prior beta0-beta2 ~ normal(mean = 0, var = 1000);
prior sigma2 ~ igamma(shape = 0.001, scale = 0.001);
random b0 ~ normal(mean = 0, var = sigma2) subject = CENTER;
eta = beta0 + b0 + beta1*trt + beta2*y0;
pi = logistic(eta);
pi0 = logistic(beta0 + b0 + beta2*y0);
model count ~ binomial(n = total, p = pi);
array or[<# of sites>];
or[1] = exp(b0 + beta1);
pooled = exp(beta1);
beta1_gt0 = beta1 > 0;
run;
```

where count = number of responders and total = number of patients.

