To include study center into the model, the study centers may be pooled according to the number of patients enrolled at each center by keeping the largest centers intact and pooling the remainder of the larger sites with smaller sites to form pooled sites. A final plan for pooling will be made and documented in Statistical Data Review meeting minutes prior to database lock. In addition, summary statistics for the ACT score will be presented at baseline, and the end of treatment and ET visits. ACT score values and changes from baseline to each visit will be summarized using descriptive statistics.

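### The only sensitivity analysis of the primary endpoint also drops centre and does not re-apply the 0.95 rule, so a small missing-data effect can be blurred

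*SAP*

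**What the plan says.** **Primary analysis (SAP 6.2.2).** The model is a Bayesian logistic regression on treatment, baseline ACT and a "random center effect of center j". Success "will be determined by a Bayesian posterior probability for" a positive treatment coefficient, with threshold 0.95. Section 2.2 makes centre the randomisation stratum. To keep centre in the model, 6.2.2 provides that "the study centers may be pooled according to the number of patients enrolled at each center". Under 4.3, patients who leave for the listed reasons (technology, product, disease worsening, adverse experience), or who leave with no early termination visit, count as failures.

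**Sensitivity analysis (SAP 6.2.3).** The protocol defers sensitivity analyses to the SAP, and the SAP gives one: "Sensitivity analysis will be performed for the primary analysis by imputing missing ACT values" under missing at random. Patients who leave because of "adverse experience or disliking the IMP will be considered having missing data", as do the other listed-reason leavers and those with no early termination visit. The imputation statement is "var trt actbase v2" and the analysis statement is "model y = trt actbase / dist = binomial". "An overall estimate will be generated using PROC MIANALYZE", from the odds ratios of 500 imputed datasets.

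**The concern.** The section sets out to vary one thing, the handling of missing ACT values. As coded, two more things change.

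1. Centre is in neither the imputation model nor the analysis model. No reason is given. Small centres do not explain it, because 6.2.2 already allows pooling.
2. The probability that the treatment coefficient exceeds zero is not computed, so the 0.95 rule is not re-applied to the imputed data.

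A reader will naturally set the two odds ratios side by side and take the gap as the effect of failure coding. In a logistic model, however, a within-centre odds ratio and one averaged over centres differ even with no missing data. With balanced dropout and a true benefit the two effects oppose each other: undoing failure coding raises the odds ratio, and dropping centre lowers it. A small real effect can therefore vanish or appear reversed. No planned run separates the two.

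**Working it through.** **Inputs from the plan.** SAP 2.4 gives response rates of 60% (CC) and 73% (DS), 150 evaluable patients per group, 30 centres, and a 95% rule described as analogous to a 1-sided 0.05 test.

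**Assumptions not in the documents.** Centre standard deviation (SD) of 0.3 to 0.7 on the logit scale. Listed-reason dropout by arm (DS/CC) of 3%/3%, 5%/5%, 10%/5% or 3%/7%, unrelated to outcome. That is a simplification, because disease worsening is a listed reason. Five patients per arm in each centre; no baseline ACT slope.

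**1. The plan's own figure.** With pooled rate 0.665, the null standard error is √(0.665 × 0.335 × 2/150) = 0.0545. The alternative standard error is √((0.60 × 0.40 + 0.73 × 0.27)/150) = 0.0540. Power = Φ((0.13 − 1.645 × 0.0545)/0.0540) = 0.77, as stated. The rates and the 1-sided reading of the rule are confirmed.

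**2. Effect of dropping centre alone, no missing data.** Without centre, the odds ratio is (0.73/0.27)/(0.60/0.40) = 1.802. With a normal centre effect that gives the same overall rates (Gauss-Hermite quadrature), the within-centre odds ratio is 1.823, 1.860 and 1.912 at SD 0.3, 0.5 and 0.7.

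**3. Large-sample odds ratios at SD 0.5.** With dropout proportions d (DS) and c (CC), failure coding multiplies the response probability by (1 − d) and (1 − c). A bridge (failure coding, no centre) is odds(0.73(1 − d))/odds(0.60(1 − c)). At 3%/3% this is (0.7081/0.2919)/(0.582/0.418) = 1.742. The primary column is the large-sample random-intercept fit.

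| Dropout DS/CC | Primary | Bridge | Missing at random, with centre | 6.2.3 as written |
|---|---|---|---|---|
| 3%/3% | 1.790 | 1.742 | 1.860 | 1.802 |
| 5%/5% | 1.749 | 1.707 | 1.860 | 1.802 |
| 10%/5% | 1.467 | 1.445 | 1.860 | 1.802 |
| 3%/7% | 1.980 | 1.922 | 1.860 | 1.802 |

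Differences between columns:

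| Dropout DS/CC | Like-for-like shift | Shift as written | Shift from the bridge |
|---|---|---|---|
| 3%/3% | 1.860 − 1.790 = +0.070 | 1.802 − 1.790 = +0.012 | 1.802 − 1.742 = +0.060 |
| 5%/5% | +0.111 | +0.053 | +0.095 |
| 10%/5% | +0.393 | +0.335 | +0.357 |
| 3%/7% | −0.120 | −0.178 | −0.120 |

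If centres are pooled in pairs, the 3%/3% values become 1.764 (primary) and 1.829 (with centre). A shift of 0.065 then shows as 1.802 − 1.764 = 0.038, so the loss is 0.027 instead of 0.058.

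**4. How often the comparison points the wrong way.** There were 2,000 simulated trials per setting with 30 unpooled centres. Fitting was by maximum likelihood, and complete cases stood in for imputation. The direction is wrong when the sign of (as written − primary) on the log odds ratio differs from the sign of (missing at random with centre − primary).

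| Dropout DS/CC | SD 0.3 | SD 0.5 | SD 0.7 |
|---|---|---|---|
| 3%/3% | 8% | 17% | 30% |
| 5%/5% | 6% | 12% | 24% |
| 3%/7% | 4% | 9% | 15% |
| 10%/5% | 0.4% | 0.8% | 2.1% |

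Measured from the bridge instead of the primary, the rate is 0.2% to 6.0% in every setting.

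**5. Effect on the verdict.** Under missing at random, dropping centre changed the 0.95 verdict (z > 1.645) in 0.1% to 2.5% of trials. Mean z was 2.26 to 2.41 with centre and 2.24 to 2.36 without.

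**6. Bayesian or frequentist.** Using the SAP's priors, 200 trials in each of six settings gave a largest difference of 0.019 in the log odds ratio between the Bayesian and maximum-likelihood primary fits. The verdict differed in at most 0.5% of trials. The framework change is not a source of bias; it only affects what is reported.

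**7. A separate simulation** (400 trials per setting, SD 0.25, 0.5, 0.75 and 1.0, 5% dropout in each arm) gave a true log odds ratio shift of +0.06 to +0.08. The visible shift was +0.05, +0.03, 0.00 and −0.03. Over all its settings, 9% to 13% of trials had a 6.2.3 result that met the 0.95 rule while a two-sided 95% interval still included 1.

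**The case against.** The case against is about materiality, and much of it stands. The success decision rests on the primary analysis alone. The usual question for a sensitivity analysis is whether the conclusion holds, and dropping centre rarely changes it. At 3%/3% and SD 0.5 the true shift is log(1.860/1.790) = 0.038, about one seventh of a standard error of 0.26 to 0.28. All four large-sample examples at SD 0.5 keep the right sign. The centre SD and the dropout split are assumed; at SD 0.3 the centre effect is only log(1.823/1.802) = 0.012, and pooling centres reduces the blur. The 1-sided answer can also be worked out from the pooled estimate and its standard error, although the SAP does not plan to report it.

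Two further limits apply. The effect of leaving centre out of the imputation model alone was not measured, because complete cases stood in for imputation. And centre as a class variable in PROC MI is a fixed effect, so that step would not match the primary's random effect exactly.

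These points set the severity. They do not remove the mismatch: the plan's only robustness check does not isolate the assumption it was written to test.

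**Conclusion.** The concern holds, as a minor one. That centre is absent from both models and that the 0.95 rule is not re-applied follow directly from the text. The size of the blur is conditional on the assumed centre SD and dropout split. It matters when the missing-data effect is small and dropout is similar in the two arms. It is negligible when centres hardly differ, and it does not hide a large, unbalanced effect: at 10%/5% a shift of 0.393 still shows as 0.335. The error has a root mean square of 0.02 to 0.07 on the log odds ratio, against a standard error of 0.26 to 0.28. The missing 0.95 assessment is a gap in reporting, not a bias.

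**What to change.** **Preferred.** Add centre, pooled as for the primary, to the class and var statements of PROC MI, placed before the Visit 2 ACT. Fit the random-centre model of 6.2.2 to each imputed dataset and combine equal numbers of posterior draws. Report the probability of a positive treatment coefficient, and the odds ratio with its 95% credible interval, beside the primary result. The cost is computing time: MCMC runs once per imputed dataset, so fewer than 500 imputations or chains shorter than 500,000 may be needed, which adds Monte Carlo error.

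**Cheaper minimum.** Run the same no-centre GENMOD model once on the failure-coded data and report it as a bridge. Primary to bridge then shows the change of centre handling and framework; bridge to 6.2.3 shows the missing-data change. Report the pooled 1-sided p-value against 0.05 as well. This is one extra run, but it does not recompute the posterior probability.

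**Optional.** As a further supportive analysis, use the observed early termination ACT of listed-reason leavers.

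Each option needs a SAP amendment before database lock, for which 2.5.2 provides, and some code. No new data are needed. Withdrawals with reasons are already tabulated by group under 5.1 and 5.2, so no new table is needed.

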6.3. Secondary Endpoints and Analysis

6.3.1. Secondary Endpoint #1 – Description of Asthma Management Actions by the Investigational Center Healthcare Providers

6.3.1.1. Definition

Secondary endpoint #1 will describe the frequency and types of interventions done to improve asthma control including:

- number of discussions between patient and HCP regarding inhaler technique or adherence
- number of therapy adjustments including:
 - increased or decreased doses of inhaled medication
 - change to different inhaled medication
 - additional inhaled medication
 - addition of a systemic corticosteroid medication for asthma or another controller, including a LAMA or biologics

- frequency of intervention to manage comorbid conditions associated with poor asthma control (GERD, sinusitis, etc.)

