9.5.2. Secondary Endpoints

Secondary endpoint #1 is the frequency and types of interventions done to improve asthma control including:

- number of discussions between patient and iHCP regarding inhaler technique or adherence
- number of adjustments of therapy including:
 - increased or decreased doses of inhaled medication
 - change to different inhaled medication
 - additional inhaled medication
 - addition of a systemic corticosteroid medication for asthma or another controller, including a LAMA or biologics
- frequency of intervention to manage comorbid conditions associated with poor asthma control (GERD, sinusitis, etc.)

Secondary endpoint #2 is the change from baseline in the mean weekly SABA usage and the change from baseline in the number of SABA-free days over the 12-week treatment period for the DS group.

Secondary endpoint #3 is the assessment of the DS (eMDPI, App and dashboard) acceptability and usability, utilizing the SUS, completed by the patients in the DS group, 18 years of age or older, and investigational center personnel at the end of the study.

Secondary endpoint #4 is the assessment of patients' beliefs and perceptions about their disease and treatment, utilizing the BMQ and the BIPQ for both the DS and CC groups, patients 18 years of age or older, describing their behavioral profile at baseline and at the end of the study.

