A Clinically Driven Assessment, which can either be via telephone or an on-site visit, may be performed at any time during the study at the patient's request and as deemed necessary by the investigator. For DS patients, the investigator will have access to information from the Albuterol eMDPI on the patient's SABA use and inhalation technique through the dashboard. If the investigator meets with or calls the patient as a result of an interaction with the dashboard, this will be captured as a Clinically Driven Assessment.

The date and reason for the Clinically Driven Assessment (eg, treatment step up, treatment step down, adherence discussion, treatment for an asthma exacerbation, or other clinical encounters generated by the data from the Albuterol eMDPI), as well as any other data obtained from procedures and assessments, will be recorded in the patient's source documents and the case report form (CRF) for patients in both groups, during the 12-week treatment period.

The following procedures and assessments will be performed at a Clinically Driven Assessment:

- conduct adverse events and adverse device effects inquiry
- conduct concomitant medication inquiry
- iHCP asks Asthma Management questions
- dispense Albuterol eMDPI, as needed (if on-site and necessary)

Other procedures and assessments may be performed at the discretion of the investigator.

5. Procedures for an Unscheduled Investigational Medicinal Product Dispensing Visit

The following procedures and assessments will be performed at an unscheduled IMP dispensing visit:

- conduct adverse events and adverse device effects inquiry
- conduct concomitant medication inquiry
- perform Albuterol eMDPI collection and accountability
- dispense test investigational medicinal product (IMP) to DS group patients

6. Procedures for Follow-up Telephone Call (Day 98 + 7 days)

The following procedures and assessments will be performed at the follow-up telephone call:

- conduct adverse events and adverse device effects inquiry

- conduct concomitant medication inquiry
- for DS group patients, confirm that the patient has returned to previous asthma treatment

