6.3.1.2. Analysis

Frequency and types of interventions during the 12-week treatment period will be summarized as count data using descriptive statistics. In addition, similar Bayesian analysis specified for primary endpoint will be performed for those variables separately using Poisson regression. The suggested SAS code for the analyses is as follows:

```
proc mcmc data = x nbi = 1000 nmc = 100000 thin = 20 seed = 159 outpost = post2
  monitor = (beta0-beta3 sigma2 beta1_gt0 lambda lambda0 pooled) statistics=(summary
  intervals);
  parms beta0-beta3 0;
  parms sigma2 1;
  prior beta0-beta3 ~ normal(mean = 0, var = 1000);
  prior sigma2 ~ igamma(shape = 0.001, scale = 0.001);
  random b0 ~ normal(mean = 0, var = sigma2) subject = CENTER;
  eta = beta0 + b0 + beta1*trt + beta2*logt + beta3*y0;
  lambda = exp(eta);
  lambda0 = exp(beta0 + b0 + beta2*logt + beta3*y0);
  model hosp ~ poisson(lambda);
  array lmda[<# of sites>];
  lmda[CENTER] = exp(b0 + beta1 + beta2*logt + beta3*y0);
  pooled = exp(beta1);
  beta1_gt0 = beta1 < 0;
run;
```

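### Secondary endpoint #1 pools increases and decreases in inhaled-medication dose in one unsigned count, and the SAP plans no split by direction

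*SAP*

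**What the plan says.** Protocol 9.5.2 introduces the endpoint with "Secondary endpoint #1 is the frequency and types of interventions done to improve asthma control including", and SAP 6.3.1.1 with "Secondary endpoint #1 will describe the frequency and types of interventions done to improve asthma control including". Three groups of actions follow: discussions of technique or adherence, therapy adjustments, and management of comorbid conditions. The second group is headed "number of therapy adjustments including" and has four sub-items. The first is "increased or decreased doses of inhaled medication". The other three are a switch of inhaled product, an added inhaled product, and an added systemic corticosteroid or other controller.

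SAP 6.3.1.2 states: "Frequency and types of interventions during the 12-week treatment period will be summarized as count data using descriptive statistics". It then adds that a "similar Bayesian analysis specified for primary endpoint will be performed for those variables separately using Poisson regression". The suggested code reports the exponentiated treatment coefficient and a one-directional posterior probability for that coefficient. No signed or net dose change is defined, and direction is not mentioned.

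Three other places bear on the point:

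- Protocol 3.1 and SAP 2.1 say that one secondary aim is to describe what clinicians do with the information that the DS gives them.
- Protocol Appendix B, item 4, gives example reasons for a Clinically Driven Assessment, among them "treatment step up, treatment step down, adherence discussion, treatment for an asthma exacerbation". The reason is recorded in the CRF for both groups.
- Protocol 5.6 has the dose and the start and end dates of each concomitant medication recorded.

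**The concern.** Raising and lowering a dose are opposite actions, yet each adds one to the same item. That item sits under a label about improving asthma control. No clinical decision is mandated in either arm, so either direction can occur in either arm.

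A rate ratio above 1 for this item could be reported as more control-improving action under the DS when the excess is in fact dose reductions. A ratio near 1 could be reported as no effect on dosing when the arms behave differently. The SAP also goes beyond the purely descriptive analysis in Protocol 9.5.4.3: it attaches a rate ratio and a directional probability, and for a mixed-direction count neither sign of the coefficient has a fixed meaning. What is at stake is the description of dosing behaviour, which is part of what this secondary objective is for.

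**Working it through.** **1. The plan's own figure.** The documents state no rate, effect size or precision for secondary endpoint #1. The one stated operating figure is the primary-endpoint power of 0.77 (SAP 2.4: 150 per group, 60% against 73%, one-sided 0.05). It reproduces: (0.13 − 1.645 × √(2 × 0.665 × 0.335/150)) / √((0.60 × 0.40 + 0.73 × 0.27)/150) = 0.0404/0.0540 = 0.75, and Φ(0.75) = 0.77. It has no bearing on this point.

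**2. What is counted.** SAP 6.3.1.2 does not say whether the separate Poisson models are fitted to the total of therapy adjustments or to each sub-item. If to sub-items, increases and decreases share one count. If to the total, direction is diluted further by the other three sub-items. Neither reading yields a result by direction.

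**3. Algebra.** Let u and d be the increases and decreases per patient over 12 weeks, with subscript 0 for CC and 1 for DS. Ignoring the centre, time and baseline terms of the planned model, the pooled ratio is (u₁ + d₁)/(u₀ + d₀).

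- The two directions add. One increase plus one decrease is two events, not zero.
- The pooled ratio equals 1.00 only if u₁ − u₀ = −(d₁ − d₀), that is, if the DS moves the two rates in opposite directions by the same absolute amount.

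**4. Illustration.** All rates are assumed. CC is 0.20 up and 0.10 down, so the denominator is 0.30.

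| DS up / down | Ratio, up | Ratio, down | Pooled ratio |
|---|---|---|---|
| 0.30 / 0.10 | 1.50 | 1.00 | 0.40/0.30 = 1.33 |
| 0.20 / 0.20 | 1.00 | 2.00 | 0.40/0.30 = 1.33 |
| 0.25 / 0.05 | 1.25 | 0.50 | 0.30/0.30 = 1.00 |
| 0.30 / 0.05 | 1.50 | 0.50 | 0.35/0.30 = 1.17 |
| 0.30 / 0.15 | 1.50 | 1.50 | 0.45/0.30 = 1.50 |

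The first two rows describe different prescribing behaviour and give the same result. The third is full masking and the fourth partial masking. In the last row both directions rise together and nothing is hidden.

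**5. Limit on masking.** Since d₁ cannot fall below 0, a pooled ratio of 1.00 can hide an increase ratio of at most 1 + d₀/u₀. With u₀ = 0.20, that is 1.25 for d₀ = 0.05, 1.50 for d₀ = 0.10 and 2.00 for d₀ = 0.20. The rarer decreases are in CC, the less can be masked.

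**6. When pooling helps.** Take the last row, 150 per group and a normal approximation to the log rate ratio at one-sided 0.05, with standard error √(1/events in CC + 1/events in DS).

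- Pooled: 45 and 67.5 events, standard error 0.192. The chance of a positive signal is Φ(0.405/0.192 − 1.645) = 0.68.
- Increases alone: 30 and 45 events, standard error 0.236. The chance is Φ(0.405/0.236 − 1.645) = 0.53.

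The combined count is therefore worth keeping.

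**The case against.** The strongest case against is that this is one of four therapy-adjustment sub-items. It belongs to a secondary endpoint that the protocol analyses descriptively, in a feasibility study with no decision rule attached to it. The other three sub-items carry much of the escalation information. The objective is neutral, to describe management actions, and decreases fall within it. The SAP promises a summary of types as well as frequency, which leaves room for a table by direction. Its Poisson code is only suggested, with a placeholder response variable. Patients enter with an ACT score below 19, so decreases may be few. The illustrative rates are assumptions, and those giving exactly 1.00 were chosen to do so.

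Most of this stands and limits the weight of the point. It does not remove it: room for a split is not a commitment to one, and the ambiguity in the first two rows of the table needs no cancellation.

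A reader might infer that step-ups and step-downs offset each other in the count, so that the DS effect on prescribing cannot be read at all. The documents do not support that. The analysis is of counts, in which the two directions sum. Only opposite between-arm effects can mask each other, and the other prescribing actions are listed separately.

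A reader might also infer that direction is already captured throughout. Appendix B shows it only as example reasons for a Clinically Driven Assessment, and a step up there could be an added controller rather than a dose increase. The response options of the Asthma Management questions, which are also asked at Visit 2, are not shown.

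**Conclusion.** The point holds as a minor one. Followed as written, the plan gives a dose-change result whose direction cannot be interpreted. An excess in the DS group could be escalation or de-escalation, and opposite effects could partly or fully mask each other. The documents give no rates from which to estimate how large the ambiguity will be. On the assumed rates above, two different patterns share a pooled ratio of 1.33, and a third pattern, with separate ratios of 1.25 and 0.50, gives 1.00. Masking matters less the rarer decreases are.

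The effect is confined to one item of secondary endpoint #1. The primary endpoint is unaffected. This is a reporting point and passes no judgement on any prescribing decision.

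A reader might go further and conclude that decreases should be removed from the count because they do not improve control. The documents do not support that: the protocol's endpoint definition includes them, and the objective is to describe actions in either direction.

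**What to change.** Amend SAP 6.3.1.1 and 6.3.1.2 before database lock, which is the deadline that SAP 2.5.2 sets for amendments:

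- Tabulate dose increases and dose decreases of inhaled medication as separate rows by treatment group.
- Fit the planned Poisson model to each.
- Keep the combined count alongside, so that the protocol definition is still reported in full.
- Take direction from the Asthma Management and Clinically Driven Assessment CRF data. Where it is not captured there, derive it from the concomitant-medication doses and dates recorded under Protocol 5.6.

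The cost is two extra rows and two more runs of existing code, plus a check of the CRF and possibly a derivation from the medication records. The main downside is sparse decreases. At the assumed 0.10 (CC) and 0.05 (DS) per patient there would be 15 and 7.5 events, giving a standard error of √(1/15 + 1/7.5) = 0.447 for the log ratio. The approximate 95% interval around 0.50 is then 0.50 × exp(±1.96 × 0.447), or 0.21 to 1.20. An interval that wide should be read as descriptive.
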